4.2. Statistical Hypotheses

No formal hypotheses will be tested. The number of proposed participants is considered sufficient to provide a descriptive summary of the safety, reactogenicity and immunogenicity of different dose levels of mRNA-1011.1, mRNA-1011.2, and mRNA-1012.1.

4.3. Sample Size and Power

Approximately 700 participants will be randomized in this study, with approximately 100 participants into each of Vaccination Groups 1-7 (≥ 50 to ≤ 75 years of age). Details regarding the number of participants in each vaccination group are presented in [Table 1](#). The probability of AEs based on sample size is presented in [Table 2](#). With 100 participants in each group receiving the study intervention, there is an approximately 87% probability to observe at least 1 participant with an AE if the true incidence of the AE is 2%; if the true incidence rate is 3%, then the probability to observe an AE is approximately 95%.

Table 2: Probability of AEs Based on Sample Size

n	True AE Rate	Probability of 0 AE	Probability of at Least 1 AE Observed
100	1.0%	36.6%	63.4%
100	2.0%	13.3%	86.7%
100	3.0%	4.8%	95.2%
100	4.0%	1.7%	98.3%

4.4. Randomization

Randomization will be performed using an interactive response technology (IRT) system.

The Sponsor's Biostatistics Department or designee will generate the randomized allocation schedule(s) for vaccination group assignment. Overall, approximately 700 healthy adults will be randomized in parallel into 7 treatment arms to receive either mRNA-1011.1, mRNA-1011.2, and mRNA-1012.1 candidate seasonal influenza vaccines or mRNA-1010 control (mRNA-1010, mRNA-1010.2, and mRNA-1010.3) vaccines, with approximately 100 healthy adult participants randomly assigned to each of vaccination groups 1 to 7. Different dose levels will be assessed in parallel (Table 1). Randomization will be stratified by influenza vaccination status in the previous influenza season (received or not received).

4.5. Blinding and Unblinding

This is an open-label study.

5. Analysis Sets**5.1. Randomization Set**

The Randomization Set consists of all participants who are randomly assigned.

5.2. Full Analysis Set

The Full Analysis Set (FAS) consists of all randomly assigned participants who receive the study vaccination. Participants will be analyzed according to the vaccination group to which they were randomized.

5.3. Per-Protocol Set

The Per-Protocol (PP) Set consists of all participants in the FAS who comply with the injection schedule, comply with the timings of immunogenicity blood sampling to have a baseline and at least the Day 29 post-injection assessment (-7 / +14 days of Day 29), have no RT-PCR-confirmed influenza infection prior to Day 29 visit (Day 29 immunogenicity

assessment+7 days) and have no major protocol deviations that impact the immune response. The PP Set will be used as the primary analysis set for analyses of immunogenicity unless otherwise specified. Participants will be analyzed according to the group to which they were randomized.

Participants with a dosing error will be considered as having a protocol deviation. However, the determination of whether to include/exclude participants from the PP Set due to dosing error will be based on the dosage difference (in μg) between the actual dose received and the randomized dose. The PP Set exclusion criteria for participants with dosing error are described in [Table 3](#).

Table 3: PP Set Exclusion Criteria for Dosing Errors

Group Name	Exclusion Conditions
mRNA-1011.1 50 μg	Any mRNA-1011.2 received, any mRNA-1012.1 received, any mRNA-1010 (Darwin) (Control) received, any mRNA-1010.2 (Newcastle) (Control) received, any mRNA-1010.3 (Hong Kong) (Control) received, mRNA-1011.1 received $\leq 37.5 \mu\text{g}$, or mRNA-1011.1 received $> 75 \mu\text{g}$
mRNA-1011.2 40 μg	Any mRNA-1011.1 received, any mRNA-1012.1 received, any mRNA-1010 (Darwin) (Control) received, any mRNA-1010.2 (Newcastle) (Control) received, any mRNA-1010.3 (Hong Kong) (Control) received, mRNA-1011.2 received $\leq 30 \mu\text{g}$, or mRNA-1011.2 received $> 60 \mu\text{g}$
mRNA-1012.1 50 μg	Any mRNA-1011.1 received, any mRNA-1011.2 received, any mRNA-1010 (Darwin) (Control) received, any mRNA-1010.2 (Newcastle) (Control) received, any mRNA-1010.3 (Hong Kong) (Control) received, mRNA-1012.1 received $\leq 37.5 \mu\text{g}$, or mRNA-1012.1 received $> 56.25 \mu\text{g}$
mRNA-1012.1 62.5 μg	Any mRNA-1011.1 received, any mRNA-1011.2 received, any mRNA-1010 (Darwin) (Control) received, any mRNA-1010.2 (Newcastle) (Control) received, any mRNA-1010.3 (Hong Kong) (Control) received, mRNA-1012.1 received $\leq 56.25 \mu\text{g}$, or mRNA-1012.1 received $> 93.75 \mu\text{g}$
mRNA-1010 (Darwin) (Control) 50 μg	Any mRNA-1011.1 received, any mRNA-1011.2 received, any mRNA-1012.1 received, any mRNA-1010.2 (Newcastle) (Control) received, any mRNA-1010.3 (Hong Kong) (Control) received, any mRNA-1010 (Darwin) (Control) received $\leq 37.5 \mu\text{g}$, or any mRNA-1010 (Darwin) (Control) received $> 75 \mu\text{g}$
mRNA-1010.2 (Newcastle) (Control) 50 μg	Any mRNA-1011.1 received, any mRNA-1011.2 received, any mRNA-1012.1 received, any mRNA-1010 (Darwin) (Control) received, any mRNA-1010.3 (Hong Kong) (Control) received, mRNA-1010.2 (Newcastle) (Control) received $\leq 37.5 \mu\text{g}$, or mRNA-1010.2 (Newcastle) (Control) received $> 75 \mu\text{g}$

mRNA-1010.3 (Hong Kong) (Control) 50 µg	Any mRNA-1011.1 received, any mRNA-1011.2 received, any mRNA-1012.1 received, any mRNA-1010 (Darwin) (Control) received, any mRNA-1010.2 (Newcastle) (Control) received, mRNA-1010.3 (Hong Kong) (Control) received \leq 37.5 µg, or mRNA-1010.3 (Hong Kong) (Control) received $>$ 75 µg
---	---

Note: For any missing injection, the dose is considered to be 0.0 µg and included in the lower category (' \leq x.x µg').

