6.2.4. Prior and Concomitant Medications

Prior and concomitant medications and non-study vaccinations will be coded using the World Health Organization drug dictionary (WHODD) version September 2022 or later. The summary of concomitant medications will be based on the Safety Set. Categorization of prior, concomitant, and post medications is summarized in [Table 5](#).

Table 5: Prior, Concomitant, and Post Categorization of a Medication

Medication Start Date	Medication Stop Date		
	< Injection Date	≥ Injection Date and ≤ Injection Date + 27 days	> 27 Days After Injection [1]
< Injection Date [2]	P	P, C	P, C, A
≥ Injection date and ≤ 27 days after injection	-	C	C, A
> 27 days after injection	-	-	A

P: Prior, C: Concomitant, A: After/Post

[1] includes medications with completely missing end date

[2] includes medications with completely missing start date

The number and percentage of participants using concomitant medications and non-study vaccinations during the 7-day follow-up period (i.e., on the day of injection and the 6 subsequent days) and during the 28-day follow-up period after the injection (i.e., on the day of injection and the 27 subsequent days) will be summarized by vaccination group as follows:

- Any concomitant medications and non-study vaccinations within 7 days post-injection

- Any concomitant medications and non-study vaccinations within 28 days post-injection
- Seasonal influenza or Coronavirus Disease 2019 (COVID-19) vaccine within 28 days post-injection
- Antipyretic or analgesic medication within 28 days post-injection

A summary table of concomitant medications and non-study vaccinations that continued, were newly received, or were received after the injection through 28 days will be provided by PT in descending frequency based on the mRNA-1012.1 62.5 µg group.

Medications to treat or prevent fever or pain will be collected in the eDiary, and summaries will be provided based on the Solicited Safety Set by vaccination group.

Prior, concomitant, and post medications and non-study vaccinations will be presented in a listing. Medications to treat or prevent fever or pain will also be presented in a listing.

Concomitant procedures will be presented in a listing.

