6.5. Immunogenicity Analysis

The analyses of immunogenicity will be based on the PP Set. If the number of participants in the FAS and PP Set differs (defined as the difference divided by the total number of participants in the PP Set) by more than 10%, supportive analyses of immunogenicity may be conducted using the FAS.

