6.5.2. Immunogenicity Analysis

The following immunogenicity endpoint will be evaluated:

- GMT and GMFR, comparing Day 29 with Day 1 (baseline), and percentage of participants with seroconversion, defined as a postbaseline titer $\geq 1:40$ if baseline is

<1:10 and a 4-fold or greater rise if baseline is $\geq 1:10$ in anti-HA antibodies measured by HAI assay.

For the immunogenicity endpoints, the geometric mean (GM) of specific antibody titers with corresponding 95% CI at each timepoint and the GMFR of specific antibody titers with the corresponding 95% CI at each post-baseline timepoint over pre-injection baseline at Day 1 will be provided by vaccination group. For each vaccination group, all influenza strains will be tested.

Descriptive summary statistics, including median, minimum, and maximum, will also be provided. The GM will be calculated using the following formula ([Nauta 2011](#)):

$$2^{\left\{ \frac{\sum_{i=1}^n \log_2(t_i)}{n} \right\}}$$

where t_1, t_2, \dots, t_n are n observed immunogenicity titers or levels.

The GMFR measures the changes in immunogenicity titers or levels within participants. The GMFR will be calculated using the following formula:

$$2^{\left\{ \frac{\sum_{i=1}^n \log_2(v_{ij}/v_{ik})}{n} \right\}} = 2^{\left\{ \frac{\sum_{i=1}^n \log_2(v_{ij}) - \log_2(v_{ik})}{n} \right\}}$$

where, for n participants, v_{ij} and v_{ik} are observed immunogenicity titers or levels for participant i at timepoints j and $k, j \neq k$.

The 95% CIs for GMT and GMFR will be calculated based on the t distribution of the log-transformed values then back transformed to the original scale for presentation, unless otherwise specified.

For summarizations of GMT and GMFR, antibody titers reported as below LLOQ will be replaced by $0.5 \times \text{LLOQ}$. Values that are greater than the ULOQ will be converted to the ULOQ.

The model-based GM titer will be estimated based on an analysis of covariance (ANCOVA) model. In the ANCOVA model, the log-transformed antibody titer at the post-baseline timepoint (Day 29) will be treated as the dependent variable with the vaccination group as the explanatory variable and influenza vaccination status in the previous influenza season (received or not received) and the log-transformed baseline antibody titer as the covariates.

The GMT will be estimated by the geometric least square mean (GLSM) from the ANCOVA model for each vaccination group and corresponding 95% CI will be provided.

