For each between-group comparison in Table 6, the GMTR (i.e. ratio of GMTs) between the two vaccination groups at Day 29 will be estimated from the ANCOVA model, with 95% CI provided accordingly.

Seroconversion rate from baseline will be provided with a 2-sided 95% CI using the Clopper-Pearson method at each post-baseline timepoint. For HA, the rate of seroconversion is defined as the proportion of participants with either a pre-vaccination HAI titer < 1:10 and a post-vaccination HAI titer \geq 1:40 or a pre-vaccination HAI titer \geq 1:10 and a minimum 4-fold rise in post-vaccination HAI antibody titer.

For each between-group comparison specified in Table 6, the difference of seroconversion rates between the two vaccination groups at Day 29 for each applicable pair will be provided along with 95% CIs estimated using Miettinen-Nurminen method.

Table 6: Between-Group Immunogenicity Comparisons

Control Arm	Treatment Arm			
	mRNA-1011.1 50 μ g	mRNA-1011.2 40 μ g	mRNA-1012.1 50 μ g	mRNA-1012.1 62.5 μ g
mRNA-1010 (Darwin) 50 μ g	X	X	X	X
mRNA-1010.2 (Newcastle) 50 μ g	X	X	X	X
mRNA-1010.3 (Hong Kong) 50 μ g	X	X	X	X
mRNA-1011.2 40 μ g	X	NA	X	X

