6.6. Exploratory Analyses

The below exploratory analyses of immunogenicity may be performed:

- GMT, GMTR (mRNA-1011.1, mRNA-1011.2, and mRNA-1012.1 against mRNA-1010), and GMFR (compared with Day 1) of anti-HA as measured by HAI assay.
- GMT and GMFR (compared with Day 1) of anti- HA antibodies as measured by MN assays or other alternative methods against vaccine matched strains.
- GMT and GMFR (compared with Day 1) of anti- HA antibodies as measured by HAI or MN assays against vaccine-mismatched strains.

- Frequency, magnitude, and phenotype of virus-specific B-cell responses measured by flow cytometry or other methods, and to perform targeted repertoire analysis of B cells after vaccination.
- Frequency of RT-PCR-confirmed ILI and assessment of immune responses in participants with RT-PCR-confirmed ILI.

In the ANCOVA model, the log-transformed antibody titers at each available post-baseline timepoint (Day 29 and Day 181/EoS) are treated as the dependent variable, with the treatment group as the explanatory variable and influenza vaccination status in the previous influenza season (received or not received) and the log-transformed baseline antibody titer as the covariates.

An NP swab specimen for viral respiratory pathogens will be collected prior to the study intervention administration on Day 1. Throughout the study, the participant will be instructed to contact the study site if he/she has symptoms suggestive of ILI. An unscheduled visit for symptom assessment and NP swab for viral respiratory pathogens will be conducted if a participant has protocol-defined ILI ≤ 7 days of symptom onset.

The frequency of RT-PCR-confirmed ILI, including RT-PCR-confirmed protocol-defined influenza infection and RT-PCR-confirmed CDC-defined influenza infection, is an exploratory efficacy endpoint. A participant may have multiple RT-PCR results for influenza post-baseline and is counted as positive if the participant had at least one positive post-baseline result for influenza. The following outputs will be provided for RT-PCR-confirmed ILI based on the FAS:

- The number and percentage of participants with negative, positive, and inconclusive/invalid RT-PCR test results for influenza at baseline and post-baseline will be summarized by vaccination group.
- Participants with baseline and post-baseline positive RT-PCR results for influenza will be presented in a listing.

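### The single PP Set stops guarding against influenza infection and licensed influenza vaccines at about Day 29, yet it also supplies the Day 181 HAI summaries

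*SAP*

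**What the plan says.** SAP 5.3 sets PP membership once per participant. Members must "have no RT-PCR-confirmed influenza infection prior to Day 29 visit", with the cut-off extended to seven days after the Day 29 immunogenicity sample. They must also have no major deviation that affects the immune response; SAP 6.2.6 leaves the deviation rules to be settled before database lock.

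Protocol 6.7.3 lists products that may affect PP evaluability. A licensed or authorized vaccine counts only in the 28 days after dosing. Investigational or non-registered products, chronic immunosuppressants, immunoglobulins, long-acting biologics and blood products count throughout the study. Protocol 5.3 asks participants to put off licensed vaccines only until the Day 29 Visit is done.

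SAP 6.5 then applies this set generally: "The analyses of immunogenicity will be based on the PP Set". SAP 6.5.2 calls for GMTs at each timepoint and "the GMFR of specific antibody titers with the corresponding 95% CI at each post-baseline timepoint over pre-injection baseline at Day 1", and adds: "Seroconversion rate from baseline will be provided with a 2-sided 95% CI using the Clopper-Pearson method at each post-baseline timepoint". It also says: "For each vaccination group, all influenza strains will be tested". In the optional ANCOVA of SAP 6.6, "the log-transformed antibody titers at each available post-baseline timepoint (Day 29 and Day 181/EoS) are treated as the dependent variable". The final study report covers immunogenicity through Day 181 (SAP 6.8.2).

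Two listings are planned: "Participants with baseline and post-baseline positive RT-PCR results for influenza will be presented in a listing" (SAP 6.6) and "Prior, concomitant, and post medications and non-study vaccinations will be presented in a listing" (SAP 6.2.4). SAP 6.6 also allows an assessment of immune responses in participants with RT-PCR-confirmed ILI.

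**The concern.** The infection and sampling criteria of the PP Set are built around Day 29, but the set is carried unchanged to a visit five months later. A participant who has influenza, or receives a licensed influenza vaccine, between those visits stays in the set, and the Day 181 titer then reflects that exposure as well as the study vaccine. Within-arm Day 181 GMT, GMFR and seroconversion could look higher than the study vaccine alone would produce, under a per-protocol label. Because SAP 6.5.2 has every strain tested in every group, the effect would be strain by strain, and one exposure need not raise all strains equally.

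The boundary is also uneven. A licensed influenza vaccine at Day 100 has no bearing on PP evaluability, while an investigational one at Day 100 may. Both could raise HAI titers.

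**Working it through.** **No figure to reproduce.** The plan gives no number on this point. Its only sample-size calculation, the chance of seeing at least one AE, does not bear on it.

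**Time without a guard (nominal schedule).** Infection: the guard ends at Day 29 + 7 = Day 36, leaving 181 − 36 = 145 of 180 days (81%). Licensed vaccine: the guard ends 28 days after dosing, leaving about 181 − 28 = 153 of 180 days (85%).

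**Which rule could act on a Day 181 titer?**

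| Exposure after about Day 36 | Rule on PP evaluability |
|---|---|
| Investigational influenza vaccine | Protocol 6.7.3, whole study |
| Chronic immunosuppressants, immunoglobulins, long-acting biologics, blood products | Protocol 6.7.3, whole study |
| Licensed influenza vaccine | None; the 28-day limit has passed |
| RT-PCR-confirmed influenza | None; the SAP 5.3 limit has passed |

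The major-deviation clause does not fill the last two rows: an infection is not a deviation, and neither is a licensed vaccine given after the Day 29 Visit. SAP Appendix A only maps samples to visits. The listings and the possible ILI immune-response assessment identify or describe these participants but remove no titer. The supportive FAS analysis is conditional and contains the same titers.

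**Size for GMT and GMFR.** All inputs are assumptions. If a share p of an arm has the titer to a given strain raised k-fold, the GMT, and hence the GMFR, is multiplied by k^p.

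| k | p=1% | 2% | 5% | 10% | 20% |
|---|---|---|---|---|---|
| 2 | 1.007 | 1.014 | 1.035 | 1.072 | 1.149 |
| 4 | 1.014 | 1.028 | 1.072 | 1.149 | 1.320 |
| 8 | 1.021 | 1.042 | 1.110 | 1.231 | 1.516 |

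**Scale.** The 95% CI factor of a GMT is 2^(t·SD/√n). With n=100 and an assumed log2 SD of 1.5 or 2.0, it is 1.229 or 1.317. At k=4 the bias equals that factor when p = ln(1.229)/ln(4) = 0.149 or ln(1.317)/ln(4) = 0.199. At k=8 the shares are ln(1.229)/ln(8) = 0.099 and ln(1.317)/ln(8) = 0.132.

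**Seroconversion.** As an upper bound, let every boosted participant convert: s + p(1 − s). With an assumed s = 40%, the rate reads 40.6%, 41.2%, 43%, 46% and 52% at p = 1%, 2%, 5%, 10% and 20%.

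**Between-arm ratio.** The multiplier is k1^p1 / k2^p2.
- Equal p and k: 4^0.02/4^0.02 = 1.000
- p 2% versus 1%, k=4: 1.014
- p 10% versus 5%, k=4: 1.072
- k 8 versus 4, p=2%: 8^0.02/4^0.02 = 1.014

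**The case against.** The strongest reply is that this is a preference. Summarizing every observed titer is a legitimate choice. The PP definition matches the only immunogenicity comparison ranked above exploratory, Day 29 against Day 1. The Day 181 objective is exploratory and may not be pursued, Table 6 comparisons are at Day 29, and no hypothesis is tested. All this stands, and it fixes the reach of the point. It does not explain why protocol 6.7.3 carries other exposures through the whole study while these two stop at about Day 29.

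A second reply is that the effect may be negligible. At p of 1% to 2% and k=4 it is 1.01 to 1.03, well inside the CI factor. The dates in the SAP introduction (protocol 3 January 2023, eCRF 15 February 2023) suggest a start late in or after the northern winter, which points to few infections. But enrollment dates and duration are not given, so a licensed vaccine in the autumn before Day 181 cannot be ruled out.

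A third reply also stands: an RT-PCR rule removes only detected cases. Confirmation under protocol 8.4.1 needs defined ILI and a positive result within seven days of onset, so asymptomatic, unreported and late-swabbed infections remain. Excluding infected participants also conditions on an event after randomization that vaccination may influence.

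A reader might infer that the Day 181 PP result has no per-protocol rule at all after Day 29. The documents do not support that: the whole-study criteria of protocol 6.7.3 still apply, and the major-deviation clause has no Day 29 limit.

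**Conclusion.** The point holds as a limited gap covering two exposures. After about Day 29 the PP Set has no rule for RT-PCR-confirmed influenza or for licensed influenza vaccines, and its Day 181 summaries can carry titers raised by either. The final study report will present those summaries.

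The size cannot be fixed from the documents. Under the assumed ranges, a strain's Day 181 GMT is inflated by a factor of 1.007 (p=1%, k=2) to 1.516 (p=20%, k=8). At k=4 it is minor for shares of 1% to 2% and comparable to the CI factor only at about 15% to 20%.

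Two further inferences should be resisted. The Day 29 secondary endpoint and the Day 29 interim analysis are not affected. Nor can Day 181 ratios be called biased as they stand: equal shares and equal boosts cancel, and nothing in the documents shows a difference by arm. With an open-label design and candidates intended to improve A/H3N2 protection, a difference is possible but not established. This is a worthwhile improvement to the plan, not a threat to its main results.

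**What to change.** In SAP 5.3 and 6.5, define PP evaluability by visit:

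- Day 181 PP summaries, and the Day 181 ANCOVA if run, leave out titers drawn after RT-PCR-confirmed influenza or a non-study influenza vaccine. The participant's earlier titers stay in.
- Exclusions are tabulated by arm and reason.
- The all-titers Day 181 result is shown alongside, so that any selection from excluding infected participants is visible.
- The text says that only detected infections are removed.

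This concerns the analysis only and does not touch what participants may receive. No new data are needed: non-study vaccinations are recorded through Day 181 (protocol 6.7.2), and ILI swabs continue throughout the study (protocol 8.2.3).

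The cost is SAP wording, programming and one extra Day 181 analysis. Precision falls slightly: the log-scale CI widens by √(100/n), which is 1.005, 1.010 or 1.054 when 1, 2 or 10 of 100 titers are lost. The remaining downsides, possible selection and incomplete removal, should be stated with the results.

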5.4. Safety Set

The Safety Set consists of all randomly assigned participants who receive the study vaccination. The Safety Set will be used for analyses of safety, except for the solicited ARs. Participants will be included in the vaccination group corresponding to what they actually received according to the rules given in [Table 4](#).

Table 4: Vaccination Group Corresponding to Dose Received

Group Name	Inclusion Conditions
mRNA-1011.1 50 µg	No mRNA-1011.2 received, no mRNA-1012.1 received, no mRNA-1010 (Darwin) (Control) received, no mRNA-1010.2 (Newcastle) (Control) received, no mRNA-1010.3 (Hong Kong) (Control) received, and mRNA-1011.1 dose $>$ 0 µg
mRNA-1011.2 40 µg	No mRNA-1011.1 received, no mRNA-1012.1 received, no mRNA-1010 (Darwin) (Control) received, no mRNA-1010.2 (Newcastle) (Control) received, no mRNA-1010.3 (Hong Kong) (Control) received, and mRNA-1011.2 dose $>$ 0 µg
mRNA-1012.1 50 µg	No mRNA-1011.1 received, no mRNA-1011.2 received, no mRNA-1010 (Darwin) (Control) received, no mRNA-1010.2 (Newcastle) (Control) received, no mRNA-1010.3 (Hong Kong) (Control) received, and 0 µg $<$ mRNA-1012.1 dose \leq 56.25 µg
mRNA-1012.1 62.5 µg	No mRNA-1011.1 received, no mRNA-1011.2 received, no mRNA-1010 (Darwin) (Control) received, no mRNA-1010.2 (Newcastle) (Control) received, no mRNA-1010.3 (Hong Kong) (Control) received, and mRNA-1012.1 dose $>$ 56.25 µg
mRNA-1010 (Darwin) (Control) 50 µg	No mRNA-1011.1 received, no mRNA-1011.2 received, no mRNA-1012.1 received, no mRNA-1010.2 (Newcastle) (Control) received, no mRNA-1010.3 (Hong Kong) (Control) received, and mRNA-1010 (Darwin) (Control) dose $>$ 0 µg
mRNA-1010.2 (Newcastle) (Control) 50 µg	No mRNA-1011.1 received, no mRNA-1011.2 received, no mRNA-1012.1 received, no mRNA-1010 (Darwin) (Control) received, no mRNA-1010.3 (Hong Kong) (Control) received, and mRNA-1010.2 (Newcastle) (Control) dose $>$ 0 µg
mRNA-1010.3 (Hong Kong) (Control) 50 µg	No mRNA-1011.1 received, no mRNA-1011.2 received, no mRNA-1012.1 received, no mRNA-1010 (Darwin) (Control) received, no mRNA-1010.2 (Newcastle) (Control) received, and mRNA-1010.3 (Hong Kong) (Control) dose $>$ 0 µg

